IRB Study Number: 20161061

Intraoperative Efficacy of Suction Enabled Retraction Device in Lumbar Spine Surgery

National Clinical Trial Number: **NCT03160170**

Study Number: 20161061

Date: March 15, 2017

Principal Investigator: [name]

1) Protocol Title

Intraoperative Efficacy of Suction Enabled Retraction Device in Lumbar Spine Surgery

2) Objectives*

This is a prospective randomized controlled trial of a new surgical instrument to assess:

- Effects on operative time and efficiency of exposure in open lumbar spine cases.
- Effect on total blood loss during the exposure part of the operation.
- Rate of clogging of suction device.

3) Background*

During spinal surgery, exposure of bony anatomy requires the use of retraction, suction, and electrocautery at the same time. As three instruments are generally used – a Cobb elevator, electrocautery, and suction – an assistant is generally required or the primary surgeon has to switch between the instruments. The resultant juggling of instruments and/or reliance on an assistant can influence operating time and efficiency.

The new device, Suction-Integrated Surgical Tissue Elevator & Retractor [SISTER], is shaped like a Cobb elevator but also has a hollow core allowing suction tubing to be connected. Thus, a single hand can be used to retract and suction at the same time while the other hand separates soft tissue from the bones with electrocautery. This set up which is proposed to be more efficient will be evaluated in this study.

The device is made of high density plastic material and is disposable. The device meets FDA's Medical Device Exemption 510(k) Requirements (Please see uploaded letter from Ludwig Medical Corporation).

4) Inclusion and Exclusion Criteria*

Inclusion

English-speaking patients undergoing Lumbar One to Sacral One open instrumentation performed by attending physicians in the Departments of Neurological Surgery and Orthopedic surgery will be included.

Exclusion

- Age less than 22 years old
- Patients whose procedure will not involve instrumentation

- Patients with prior Lumbar spine surgery involving more than one level
- BMI less than 20 or greater than 35
- Patients with known bleeding conditions (ex: Factor V Leiden, Von Willebrand's,)
- Patients that routinely take anticoagulation medicine (ex. Aspirin 325mg/day, Plavix)
- Operative cases where a single surgeon performs both sides of exposure.
- Pregnant women
- Prisoners
- Adults unable to consent

5) Procedures Involved*

Patients will be selected prospectively and randomly assigned to either the control group (standard exposure technique) or the suction-integrated Cobb group. Randomization will be performed with a coin toss: “best two out of three” style. For example, if “heads” represents the “control” group, 2 out of 3 tosses resulting in “heads” will assign a given patient to the control group, and if “tails” represents the “suction-integrated Cobb group” 2 out of 3 tosses resulting in “tails” will assign the patient to the suction-integrated Cobb group. Randomization will stop once 20 subjects are enrolled in the suction-integrated Cobb group. If at that time, the control group has less than 20 subjects, all subsequent subjects will be assigned to the control group.

During the consent process, patients will be informed that a new instrument may be used during their surgery. The risks of using the device will be explained to the patient, which will include the surgeon’s discomfort when using the new instrument, or failure of the device, which may lead to a delay during the exposure phase of surgery, which could ultimately result in a longer surgery. Surgeons will be given time to become familiar with the instrument. Operative data will be collected.

In the control group, the surgeons will utilize standard exposure technique and instruments. In the suction-integrated Cobb group, surgeons will be provided with the device. Standard equipment will also be readily available in case the surgeon decides for any reason not to use the device. The device will be provided by Ludwig Medical Corporation, the manufacturers of the device.

The following data will be recorded: age, gender, BMI, spinal levels involved, overall operative time, exposure time measured from skin incision until adequate exposure is achieved by the surgeon, blood loss during the exposure, and number of times the suction had to be unclogged.

No postoperative follow up is required.

A total of 40 patients will be randomized, with twenty assigned to each group.

6) Data Management*

All study staff will be CITI certified and will be trained in handling confidential medical information. Data will be stored on a password-protected computer in a secured location. Data will be coded and each subject will be assigned a unique study number. The linking code will be stored separately and will only be accessible to the study team. Only research members approved by the IRB will have access to the data.

Power analyses has determined that 36 subjects (2 groups of 18) would be sufficient to demonstrate a significant effect. The parameters and assumptions of this analysis are as follows: an average exposure time with typical instruments of 30 (± 15) minutes, a 45% reduction in exposure time previously demonstrated in a previous small study with the new device, a 1:1 enrollment ratio for sub-groups, an alpha value of 0.05 for significance, and power value of 80%. Our proposed study size of 40 subjects will therefore confer statistical power.

7) Provisions to Monitor the Data to Ensure the Safety of Subjects

The PI will be responsible for data and safety monitoring. Any suspected or observed breach in data security will be reported to the PI and IRB.

The data collected and planned analyses are described above. Data will be collected before, during, and after each patient's surgery, and will be reviewed by study staff. The trial will be suspended if a breach of security is observed, or harm is demonstrated to subjects.

8) Withdrawal of Subjects

Subjects will be withdrawn from the study if their planned surgical procedure is cancelled or changed in such a way as to no longer meet inclusion criteria for the study. If a subject withdraws from the study, or is withdrawn from the study, the study staff will stop collecting new information about the subject. However, the study team will use the information they have already collected.

9) Risks to Subjects*

The risks associated with this study are largely those of the surgery itself. Additionally, the surgeon may not be comfortable using the new instrument, or the device may fail, which may lead to a delay during the exposure phase of the surgery. Also, as part of this research, there is a possibility of a breach of confidentiality (your private information) of your medical data. We will take adequate steps to protect your confidentiality. In addition, there may be uncommon or previously unknown risks that might occur.

10) Potential Benefits to Subjects*

Patients may benefit from a potential decrease in operative time, anesthesia time, and reduced blood loss.

11) Vulnerable Populations*

Not applicable.

12) Setting

The research will be conducted at Jackson Memorial Hospital.

13) Resources Available

All research personnel are CITI Certified.

Ludwig Medical Corporation will provide 40 devices free of charge for the study.

14) Recruitment Methods

Surgeons in the Departments of Orthopedics and Neurological Surgery will refer eligible patients to the study. Subjects for the proposed study will be those who have already decided to undergo lumbar spine surgery. Subjects will be selected prospectively based on the proposed operative plan and randomized to one of the two groups (control vs suction-integrated Cobb groups).

15) Local Number of Subjects

Forty patients will be included.

16) Confidentiality

- Data will be stored on a password-protected computer in [name] office.
- Data will be coded and each subject will be assigned a unique study number. The linking code will be stored separately and will only be accessible to the study team.
- Only those research staff members approved by the IRB will have access to all research related data.

17) Provisions to Protect the Privacy Interests of Subjects

All data necessary and sufficient for the conduct of the study will be collected and stored as described in the "Confidentiality" section. This information will be both identifiable and non-identifiable data. General information will be collected about the patients from the medical records.

18) Compensation for Research-Related Injury

If injury should occur, treatment will be available. If subjects have insurance, their insurance company may or may not pay for these costs. If subjects do not have insurance, or if their insurance company refuses to pay, subjects will be expected to pay. Funds to compensate for pain, expenses, lost wages and other damages caused by injury are not available.

19) Economic Burden to Subjects

This study involves no financial cost to subjects.

20) Consent Process

Participants in this study will have already consented to surgery prior to being approached regarding participation in the study. Any concerns with the study or information collected will be discussed with the subjects.

Prior to surgery, the patient will be approached by the Investigator or one of the Sub-Investigators who will present a sample device and describe its function as well as the goal of the study. The patient will be given an opportunity to ask any questions about the device and the study. If the patient agrees to participate, he/she will be asked to sign the consent form.

Spanish-speaking participants will not be included in this study, as at this time there are no funds to translate the consent documents.

21) Process to Document Consent in Writing

Documentation of the informed consent process will include the following information:

- Consent will be obtained prior to any study related procedures being performed. The ICF will be fully explained and any questions will be answered to the satisfaction of the subject.
- Subjects' will receive a signed copy of the ICF and HIPAA authorization forms. The ICF process will be performed in a language that the subject comprehended fluently. Specific questions asked by the subject will be documented.
- A copy of all executed ICFs and HIPAA forms will be provided to supporting programs/units/entities (e.g. JHS Medical Records and Clinical Trial Office).

22) Drugs or Devices

A company representative will bring the device to the hospital on the day of surgery for each case enrolled in the study. Institutional and legal protocols will be followed in bringing the device to the hospital. Sterile procedures will be followed in opening and employing the device.

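### Surgeon and department are neither recorded nor balanced, so the planned data set cannot show or adjust for a chance difference in operators between the arms

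*Combined protocol and SAP*

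**What the plan says.** - **Operators.** Section 4 includes cases "performed by attending physicians in the Departments of Neurological Surgery and Orthopedic surgery will be included". It excludes "Operative cases where a single surgeon performs both sides of exposure", so each case has more than one exposing surgeon. Section 14 has surgeons in both departments referring patients. The number of surgeons is not given.
- **Allocation.** Section 5: "Randomization will be performed with a coin toss", best two of three, in one sequence with no stratification or blocking. Tossing stops when the device group reaches 20. If the control group is still short of 20, "all subsequent subjects will be assigned to the control group".
- **Data.** Section 5: "The following data will be recorded: age, gender, BMI, spinal levels involved, overall operative time", then exposure time, and finally "blood loss during the exposure, and number of times the suction had to be unclogged". None of these eight items identifies a surgeon or a department.
- **Familiarity.** Section 5: "Surgeons will be given time to become familiar with the instrument". No amount, criterion or log of use follows.
- **Analysis.** Section 7 refers back to planned analyses, but the protocol contains only a power statement. It names no test, model or covariate.

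**The concern.** How quickly the spine is exposed and how much blood is lost depend partly on who operates. The protocol accepts this. It lists surgeon discomfort with the device as a possible cause of delay, it allows familiarisation time, and it lets the surgeon decide when exposure is adequate and the clock stops.

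With 40 cases from two departments, one department can easily be over-represented in one arm. The planned data set would not show this, and the analysis could not adjust for it. It also could not show whether slow device cases were a surgeon's first uses, so a null result would be hard to separate from unfamiliarity. The all-control tail adds to this: if the surgeon mix changed late in enrolment, the change would fall on one arm only.

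**Working it through.** **Inputs from the protocol.** Control exposure time 30 ± 15 minutes (± read as SD); 45% reduction, so 0.45 × 30 = 13.5 minutes; alpha 0.05; power 80%; 36 subjects stated as sufficient; 40 planned, 20 per arm.

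**Assumptions, because the protocol gives no figures.** 20 cases per department; final arms of 20 and 20; department means differing by D = 5, 10 or 15 minutes; total SD held at 15; department mix stable over enrolment.

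**1. The plan's own figure.** The two-sided normal formula gives n = 2 × [15 × (1.960 + 0.842) / 13.5]² = 19.4, so 20 per arm (40 in all). The two-sided t-test needs 21 per arm (42), and a one-sided test 16 per arm (32). The stated 36 is not reproduced. That is a separate matter and does not decide this point. At the planned 20 per arm, two-sided t-test power is 79%.

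**2. Chance of imbalance.** With 20 of 40 cases in each department and 20 of 40 allocated to the device, the number from one department in the device arm is hypergeometric (40, 20, 20):
- 12/8 or worse, either direction: 0.343
- 13/7 or worse: 0.113

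**3. Shift in the unadjusted estimate.** Shift = (difference in department share between arms) × D.

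| Split | Share difference | D = 5 | D = 10 | D = 15 |
|---|---|---|---|---|
| 12/8 | 0.20 | 1.0 min | 2.0 min | 3.0 min |
| 13/7 | 0.30 | 1.5 min | 3.0 min | 4.5 min |

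The 13/7 shifts are 11%, 22% and 33% of 13.5 minutes. For scale, the standard error is 15 × √(2/20) = 4.7 minutes and the 95% half-width is 2.024 × 4.74 = 9.6 minutes.

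**4. Type I error.** In 20,000 simulated trials per scenario, the overall error is about 5% with or without department in the model. Among null trials split 13/7 or worse, the unadjusted test is significant in about 6%, 9% or 15% for D = 5, 10 or 15.

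**5. All-control tail.** In 200,000 simulated allocations of 40 patients, the device arm reached 20 with controls still short in about 50%. An average of 5 controls then followed without randomisation.

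**6. Gain from balancing and adjusting.** Within-department SD is w = √(225 − D²/4) = 14.79, 14.14 or 12.99 minutes; department explains D²/4 ÷ 225 = 3%, 11% or 25% of the variance. In a balanced design the unadjusted within-arm variance is w² + (D²/4)(20/19) = 225.3, 226.3 or 228.0. The adjusted-to-unadjusted width ratio is w ÷ √(that variance) × t(37 df)/t(38 df), with t ratio 2.0262/2.0244 = 1.0009. This gives 0.986, 0.941 or 0.861, so intervals about 1%, 6% or 14% narrower. If D = 0 the interval is about 0.1% wider.

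Power comes from the noncentral t with 37 df and noncentrality 13.5 / (w√0.1) = 2.89, 3.02 or 3.29. The result is about 80%, 84% or 89%.

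**7. Would separate coin tosses be enough?** No. For two independent Binomial(20, 0.5) device counts, the chance that they differ by 4 or more is 0.27.

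**The case against.** The strongest reply is that patients are randomised individually. A reader might infer that operator differences bias the comparison or inflate false positives. The documents do not support that: averaged over allocations there is no such bias, and the overall error rate stays near 5%. A chance shift of 2 to 3 minutes is part of the sampling error that a standard error of 4.7 minutes already expresses. This stands. It leaves lost precision, and a trial that, once imbalanced, cannot be diagnosed or adjusted from its own data. It also assumes that the surgeon mix does not change during the all-control tail.

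A reader might also infer that an imbalance could never be discovered. That goes too far. Sections 6 and 16 keep a linking code, Section 17 draws information from medical records, and Section 5 says in general terms that operative data will be collected. The surgeon could probably be traced later. But this is not planned, and no log of each surgeon's device uses is provided for.

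Familiarisation time deserves credit. Without an amount or a record, however, its adequacy cannot be assessed.

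Finally, the figures concern departments, with an assumed even split and assumed gaps. That is a fair limit. Imbalance between individual surgeons could be larger, and adjusting for department leaves surgeon differences within a department in place.

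**Conclusion.** The concern holds as a matter of precision and of being able to check the result, not as a claim of systematic bias. The omissions are certain from the text: no surgeon or department field, no balancing, and no analysis that uses either. Their size is conditional. With 20 cases per department and arms of 20, about one trial in three has a 12/8 split or worse and about one in nine a 13/7 split or worse. The latter moves the estimate by 1.5 to 4.5 minutes if departments differ by 5 to 15 minutes. If departments hardly differ, little is lost. Since unadjusted power is only about 79% and the remedy is cheap, the change should be made.

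**What to change.** 1. Add to the Section 5 data list: department, a code for each exposing surgeon, and each surgeon's running number of device uses.
2. Replace the coin toss and the 20-subject stopping rule with concealed, randomly permuted blocks within department, closing at 40 in total. Surgeons refer patients and will know the assignments, so vary the block sizes and have the list held by someone who does not recruit. Running the present toss separately in each department would not secure balance (step 7 of the working).
3. Include department as a factor in the exposure-time and blood-loss comparisons.
4. Tabulate arm by surgeon, and show device-group times by use number. Label both as descriptive.

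**Cost.** Three case-sheet fields, a prepared allocation list and one model degree of freedom, which widens the interval by about 0.1% if departments do not differ. If the last block in a department is incomplete, the arms there may differ by up to half a block. No patients or procedures are added, and clinical care is unchanged.

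### Patients already operated on in the planned exposure can enrol, but prior surgery is neither a named recorded item nor a covariate (minor)

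*Combined protocol and SAP*

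**What the plan says.** The combined protocol and SAP enrols "English-speaking patients undergoing Lumbar One to Sacral One open instrumentation performed by attending physicians" (section 4). The only criterion on earlier operations excludes "Patients with prior Lumbar spine surgery involving more than one level". It does not ask where the earlier operation was, or whether it overlaps the field now to be opened.

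The first objective in section 2 is "Effects on operative time and efficiency of exposure in open lumbar spine cases"; exposure blood loss and clogging follow. Section 5 lists what is recorded: "age, gender, BMI, spinal levels involved, overall operative time, exposure time measured from skin incision until adequate exposure is achieved by the surgeon", then "blood loss during the exposure, and number of times the suction had to be unclogged". Prior surgery is not on that list. Section 17 adds only that "General information will be collected about the patients from the medical records", without naming items.

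On allocation, section 5 states "Randomization will be performed with a coin toss", with no stratification. No adjusted analysis is described anywhere.

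**The concern.** Every outcome except overall operative time is measured during the exposure. Whether the tissue has been opened before is a plausible influence on how long exposure takes and how much it bleeds. By restricting prior surgery at all, the plan treats it as relevant.

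The restriction counts levels, so a patient with one earlier operation at L4-L5 who now has L4-L5 instrumentation is eligible. Such patients can be mixed with first-time exposures in two arms of 20. Two things are at stake. Some precision may be lost if the factor stays in the error term. And a reader of the results could not see whether these patients were evenly divided, because nothing commits the trial to recording or tabulating them.

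**Working it through.** **Inputs from the documents.** Control exposure time 30 ± 15 minutes, with ± read as an SD; a 45% reduction, so 0.45 × 30 = 13.5 minutes; alpha 0.05, taken as two-sided; power 80% (all section 6); 20 per arm (section 5).

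**Assumed inputs, not in the documents.** A share p of patients has prior surgery in the planned exposure, and this adds d minutes. Ranges: p = 0.1 to 0.3, d = 5 to 15.

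**The plan's own figure.** Section 6 gives 36 subjects (18 per group). The normal approximation gives 2 × (15 × (1.960 + 0.842) / 13.5)² = 19.4, so 20 per arm, or 40 in total; the t-test gives 21 per arm. The 36 is not reproduced. That is a separate matter, and this point does not depend on it. At the planned 20 per arm, power is 81.2% (normal) or 79.2% (t), and the unadjusted standard error is 15 × √(2/20) = 4.74 minutes.

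**Variance due to prior surgery.** Taking the planning SD to include this variation already, the component is p(1−p)d² and its share is R² = p(1−p)d² / 225. The SD that chance imbalance contributes to the arm difference is √(2p(1−p)d²/20). The standard error with one covariate, relative to none, is √(1−R²) × √(38/37).

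| p | d (min) | p(1−p)d² | R² | Imbalance SD (min) | SE ratio |
|---|---|---|---|---|---|
| 0.1 | 5 | 2.25 | 0.010 | 0.47 | 1.008 |
| 0.3 | 5 | 5.25 | 0.023 | 0.72 | 1.002 |
| 0.1 | 10 | 9 | 0.040 | 0.95 | 0.993 |
| 0.2 | 10 | 16 | 0.071 | 1.26 | 0.977 |
| 0.3 | 15 | 47.25 | 0.210 | 2.17 | 0.901 |

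For the last two rows, normal-approximation power at 20 per arm becomes Φ(13.5/(4.74 × 0.977) − 1.96) = 83% and Φ(13.5/(4.74 × 0.901) − 1.96) = 88%.

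**How uneven the arms could be.** With two independent Binomial(20, p) arms, the chance of a difference of at least 4 affected patients is 6%, 16% and 23% at p = 0.1, 0.2 and 0.3. A difference of 4 moves the arm contrast by (4/20) × d, which is 1 to 3 minutes for d = 5 to 15, against a planned effect of 13.5.

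**If the SD of 15 excludes this variation.** The documents do not say which holds. The total SD is then √(225 + p(1−p)d²), which is 15.1 to 16.5 over the full range, and unadjusted power at 20 per arm is 81% to 73% (normal).

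**The case against.** The strongest reply is that this is a matter of preference. A level count is simple, can be checked from the chart and contradicts nothing in the documents. Allocation is by coin toss, so prior surgery causes no systematic bias. The 1.3 to 2.2 minutes of imbalance SD is a component of the 4.74-minute standard error, not an addition to it, and an ordinary test already allows for it. The documents give neither p nor d. The larger gains need d at 33% to 50% of the 30-minute mean, and at 5 minutes adjustment loses slightly. All of this stands, and it is why the point is minor.

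Several stronger readings are tempting, but the documents do not support them:

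- *The rule admits fully scarred fields and removes untouched ones.* The wording only makes this possible. The documents never mention scar and give no counts. An earlier one-level operation may have been one-sided or by another approach. The examples also need L1 to S1 to mean any levels in that range. Recording the levels involved suggests this, but it is not stated.
- *These patients cannot be identified.* Screening must already look at prior lumbar surgery, section 17 allows collection from medical records, and section 16 keeps a linking code. The accurate statement is that no one is committed to recording it.
- *The criterion should be rewritten around the planned exposure.* A rule excluding prior surgery at more than one of the levels to be exposed would still admit the L4-L5 patient above. It would also newly admit some partly re-operated fields, such as earlier surgery at L3-L5 with L5-S1 now planned. It is a trade-off, not a correction.

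What the reply does not answer is the reporting gap: section 17's unspecified general information does not commit the trial to recording or tabulating this factor.

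**Conclusion.** The point holds as a minor one. Patients with earlier surgery in the planned exposure can enrol, and neither recording nor adjustment is planned. The consequence is a modest loss of precision and an imbalance that would go undescribed. It is not a biased estimate or an invalid test.

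A reader might infer that uneven arms could pass for a device effect. At the assumed values, a 4-patient difference shifts the contrast by 1 to 3 minutes, well short of 13.5, and the test's error rate already covers such chance differences.

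For exposure time, adjustment gains about 2% to 10% in standard error at p = 0.2 to 0.3 and d = 10 to 15 minutes, under 1% at p = 0.1 and d = 10, and nothing or a loss of up to about 1% at d = 5. These figures assume that the planning SD of 15 already includes the variation. The documents give no figures from which to size the effect on blood loss or clogging.

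**What to change.** Leave the eligibility criterion as it is. In section 5:

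1. Add to the recorded data: prior surgery within the planned exposure (yes/no), taken from the chart and recorded before the coin toss. Subjects sent to control without a toss, once the device arm has reached 20, should have it recorded before assignment too.
2. State that it will be reported by arm with the other baseline items.
3. Pre-specify it as a covariate in the exposure-time and exposure-blood-loss comparisons.

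The cost is one chart item that screening already has to examine and one degree of freedom. If the factor turns out to matter little, the standard error could be up to about 1% larger than without adjustment. No treatment, visit or sample size changes.

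### Allocation is by a best-of-three coin toss with no concealed sequence, log or separate allocator required, so nothing guards against a toss being repeated or re-read after consent

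*Combined protocol and SAP*

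**What the plan says.** - **Method (Section 5).** "Randomization will be performed with a coin toss", decided by the best of three. The link between coin face and arm is given only by example: "2 out of 3 tosses resulting in “heads” will assign a given patient to the control group".
- **Filling the arms (Section 5).** "Randomization will stop once 20 subjects are enrolled in the suction-integrated Cobb group". If control is then short of 20, "all subsequent subjects will be assigned to the control group".
- **Who refers (Section 14).** "Surgeons in the Departments of Orthopedics and Neurological Surgery will refer eligible patients to the study".
- **Who operates (Section 4).** Eligible procedures are those "performed by attending physicians in the Departments of Neurological Surgery and Orthopedic surgery".
- **Who takes consent (Section 20).** Before surgery, "the patient will be approached by the Investigator or one of the Sub-Investigators". Whether these people are also the operating surgeons is not stated.
- **Order (Section 21).** Consent comes before any study-related procedure. The toss is not named.
- **Data recorded (Section 5).** The list covers patient characteristics, times, blood loss and clogging. It has no toss result, allocation time or name of the person tossing.
- **Logistics (Section 22).** "A company representative will bring the device to the hospital on the day of surgery for each case enrolled in the study".

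The document does not say who tosses, when, where or before whom. It mentions no list, envelopes or independent allocator.

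**The concern.** The surgeon knows the arm, and exposure time, the outcome on which the sample size rests, stops when the surgeon finds the exposure adequate. No stratification or covariate adjustment is described. Random allocation is therefore the main protection against a difference in case difficulty between the arms.

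A coin toss at the point of care is random only if its first result stands. Sections 5 and 9 list surgeon discomfort with the new instrument, and the delay it may cause, among the risks. A clinician who expects a hard exposure thus has an ordinary, well-meant reason to prefer standard instruments. If such cases drift to control, the device looks faster than it is. With no required record of the tosses, a later reader could not show that this did not happen.

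**Working it through.** **1. The toss itself.** With probability p per toss, best of three gives 3p² − 2p³. At p = 0.5 this is 0.75 − 0.25 = 0.50. The rule is fair, but it adds no protection over a single toss.

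**2. What is required before and after consent.** Section 21 places consent before study-related procedures. If the toss counts as one, the patient is committed before the arm is known. From then on the document is silent: there is no witness, no record, and no bar on the surgeon tossing or seeing the toss.

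**3. Size of a plausible distortion.** The plan gives no figure for this.

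Inputs from the plan (Sections 5 and 6): 40 patients, SD 15 min, control mean 30 min and a 45% reduction, so the target is 0.45 × 30 = 13.5 min.

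Assumptions, none from the documents:
- the hardest h = 25 to 33% of cases are recognised in advance;
- a device result in such a case is re-tossed once with probability q = 0.5 to 1;
- foreseen difficulty correlates ρ = 0.5 to 0.7 with exposure time;
- steering always favours the device, there is no true effect, and the test is a pooled t test (the plan names no test).

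Formulas:
- Share of patients re-tossed = h × 0.5 × q.
- P(device | hard) = 0.5 − 0.25q.
- Extra time in hard cases D = 15ρ × φ(z)/[h(1 − h)], where z is the upper-h normal quantile and φ the normal density.
- Spurious saving ≈ D × (share of hard cases in control − share in device).

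| | Mild end (h 0.25, q 0.5, ρ 0.5) | Strong end (h 0.33, q 1, ρ 0.7) |
|---|---|---|
| Re-tossed | 0.25 × 0.5 × 0.5 = 6% | 0.33 × 0.5 × 1 = 17% |
| P(device given hard) | 0.375 | 0.25 |
| Hard share, device arm | 0.09375/0.46875 = 0.200 | 0.0825/0.4175 = 0.198 |
| Hard share, control arm | 0.15625/0.53125 = 0.294 | 0.2475/0.5825 = 0.425 |
| D | 7.5 × 0.318/0.1875 = 12.7 min | 10.5 × 0.362/0.2211 = 17.2 min |
| Spurious saving | 12.7 × 0.094 = 1.2 min | 17.2 × 0.227 = 3.9 min |

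Simulation (40,000 null trials per setting) gives the same savings, with two-sided type I error of about 5.5 to 12%. If both arms are capped at 20, the ranges fall to about 1.0 to 3.2 min and 5.5 to 10.5%. Across both versions the saving is about 1.0/13.5 = 7% to 3.9/13.5 = 29% of the target effect.

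**Cross-check with a cruder model.** Here 30 to 50% of cases are hard and take 10 to 20 min longer. With half of the unwanted results re-tossed, the saving is 1.1 to 2.5 min and type I error about 6 to 8%. With all re-tossed, they are 2.1 to 5.3 min and about 7 to 20%. The size depends heavily on the assumptions.

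**4. The fill rule.** A run of known control assignments occurs if at least 20 of the first 39 results are device. By symmetry the chance is 50%, and the mean length of the run, when there is one, is 5.0 patients. For those patients the arm is known before referral and consent, so envelopes would conceal nothing unless this rule is replaced as well.

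**The case against.** The strongest reply is that much of this argues from silence, and several tempting readings do go beyond the text.

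- **That nothing commits the patient before the toss.** Section 21 puts consent before study-related procedures, and assignment is naturally one of these. While the next result is unpredictable, this limits steering before enrolment. The exposure that remains is a repeated or re-read toss after consent, and the known control run in step 4.
- **That the tosses will go unrecorded.** The document requires no record. It does not say that none will be kept.
- **That surgeons enrol their own patients.** Surgeons refer, and their departments operate. Consent is taken by the Investigator or Sub-Investigators, whose overlap with the operating surgeons is not stated.
- **That steering could not be noticed at all.** Age, BMI and spinal levels are recorded, so imbalance on these would show, though its cause would not. The exclusions on BMI, prior multilevel surgery and bleeding risk also narrow foreseeable difficulty.
- **That the motive is strong.** Section 5 lets the surgeon fall back on standard equipment for any reason, which weakens the incentive to re-toss.

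These replies narrow the point without removing it. None supplies concealment, a required log or a separate allocator.

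**Conclusion.** The point holds in this form: the protocol requires no concealed sequence, no record of the tosses and no separation of the toss from the surgeons, and nothing guards against a toss being repeated or re-read after consent. Under the stated assumptions the distortion is about 1 to 4 min against a 13.5 min target, with type I error of about 5.5 to 12%. At the mild end the inflation is barely visible. These figures illustrate what the plan leaves open. They do not estimate what will happen.

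A reader might infer that allocation will be manipulated, or that the best-of-three rule is itself biased. The documents support neither: the rule is fair with a fair coin, and nothing suggests intent. The change is worth making because it is cheap and the trial has few other safeguards.

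**What to change.** In Section 5, replace both the coin toss and the rule assigning all later patients to control:

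- Generate a 20:20 list by computer before the first patient, for example with randomly varying block sizes that are not disclosed to the surgeons.
- Place it in sequentially numbered, opaque, sealed envelopes, held by existing study staff who do not refer, consent or operate on that patient. The document does not name such a person, so the protocol should.
- Write subject number, date and time on the envelope before opening it. Open it only after written consent and the final eligibility check.
- Keep every envelope, opened or not, as the audit trail.

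Late opening fits Section 22, which already has the device brought for every enrolled case.

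The cost is one protocol paragraph and about an hour of preparation. The number of patients stays at 40. The downside is small: the surgical team learns the arm later. In an open-label trial with a fixed 20:20 total, someone who counts can still deduce the last assignment or so, which is far less than a run averaging five patients.
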